Statistical Methodology	
Primary outcome PET images will be analyzed using 1) the two-tissue kinetic model to calculate total distribution volume, corrected for free fraction of radioligand in plasma (V_T/f_P), and 2) the cerebellum as a pseudo-reference region to calculate standardized uptake value ratios (SUVR). Effect size will be calculated for different regions as the difference in means (DLBD vs. controls) divided by the standard deviation.
 
Secondary outcomes Coefficient of variation (%COV = standard deviation / mean) will be calculated for controls and patients with DLBD for both V_T/f_P and SUVR data. SUVR values will be calculated using cerebellum as reference regions. Additional reference regions will be explored. Correlation coefficients will be computed to look for correlation between ^{11}C-PBR28 binding (V_T/f_P and SUVR) and clinical severity. Severity will be measured using CDR-sum of boxes, MoCA score, and UPDRS. We will also look for correlations between ^{11}C-PBR28 binding and atrophy, as determined using ROI volumes derived from MRI data.
 
Sample size determination This is a Phase 2 pilot study to determine feasibility and preliminary data for a larger study. Therefore, the proposed sample size is not expected to provide enough statistical power to see significant group differences.

CONFIDENTIAL

This material is the property of Columbia University Medical Center. Do not disclose or use except as authorized in writing by the study sponsor

1 Introduction

This document is a protocol for a human research study. This study is to be conducted according to US and international standards of Good Clinical Practice (FDA Title 21 part 312 and International Conference on Harmonization guidelines), applicable government regulations and Institutional research policies and procedures.

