^{11}C -(*R*)-PK 11195 has low specific-to-nonspecific binding[25] which could confound accurate quantification of TSPO density. The second generation TSPO radioligand ^{11}C -PBR28 has greater specific-to-nonspecific binding than ^{11}C -(*R*)-PK 11195 in monkey brain[25] and has been used to detect neuroimmune activation in stroke, schizophrenia, and epilepsy[26-28]. Therefore, ^{11}C -PBR28 PET imaging is expected to detect inflammatory changes in DLBD and may be useful for monitoring disease progression and response to novel treatments. Because the relationship between inflammation and the clinical symptoms exhibited in DLBD remains unknown, there is a critical need to determine the relationship between inflammation and DLBD to increase knowledge about the mechanisms underlying the disease and help develop antiinflammatory treatments as disease-modifying therapy for this presently incurable disorder.

One limitation of ^{11}C -PBR28, shared by all tested second generation TSPO radioligands, is differential affinity caused by the rs6971 single nucleotide polymorphism on the TSPO gene[29]. Statistical correction for TSPO genotype allows inclusion of individual heterozygous for the polymorphism; however, homozygotes have negligible binding with ^{11}C -PBR28 and must be excluded from analysis[27].

The primary research objective is to generate pilot data in patients with DLBD to more effectively design an R01 application to comprehensively study the relationship between inflammation and DLBD. The aims are to:

1. Determine feasibility of performing ^{11}C -PBR28 PET in patients with DLBD.
2. Determine effect size of ^{11}C -PBR28 binding in patients with DLBD vs. controls. The exploratory aims are:
 1. Identify potential reference regions for ^{11}C -PBR28 binding in patients with DLBD.
 2. Determine if ^{11}C -PBR28 binding correlates with cognitive impairment and Parkinsonism in patients with DLBD.

1.2 *Investigational Agent*

^{11}C -PBR28 is a PET radioligand that binds to the 18 kDa translocator protein (TSPO), a marker of inflammation. ^{11}C -PBR28 has previously been administered in humans.

This radioligand will be administered in tracer doses. ^{11}C -PBR28 will be administered at activity of up to 20 mCi per injection.

1.3 *Preclinical Data*

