These unusual subjects were initially referred to as “non-binders,” reflecting the apparently lack of interaction between ¹¹C-PBR28 and the target protein. In vitro binding assays using peripheral leukocytes isolated from blood samples taken from non-binders showed that these subjects expressed TSPO with ~50-fold lower affinity for ¹¹C-PBR28 than binders[38]. Later binding studies showed that there exist three patterns of ¹¹C-PBR28 binding in human subjects[39, 40]. High affinity binders (HABs) behave as though they express only TSPO that binds with high affinity, low affinity binders (LABs) behave as though they express only TSPO that binds with low affinity, and mixed affinity binders (MABs) behave as though they express both a high- and low-affinity version of TSPO. Genetic studies determined there is a strong association between TSPO binding status and the rs6971 (Ala147Thr) single nucleotide polymorphism on the TSPO gene[29]. HABs lack this polymorphism, LABs are homozygous, and MABs are heterozygous. As the allelic frequency of the polymorphism is 30% based on population studies, 9% are expected to be LABs. Caucasians and African Americans have highest prevalence of the polymorphism while it is rare in Han Chinese and Japanese. Our ex vivo study showed that statistical correction for TSPO genotype improves the ability of ³H-PBR28 to detect differences in TSPO density between controls and patients with schizophrenia in the dorsolateral prefrontal cortex[27]. Therefore, clinical studies have since employed the strategy of excluding LABs and performing statistical correction to remove the effect of systematic physiological differences in ¹¹C-PBR28 binding between HABs and MABs.

1.4.1.4. ¹¹C-PBR28 in Alzheimer’s disease

In our first AD PET study using ¹¹C-PBR28, we found that AD patients had greater binding than MCI patients or controls[41]. The largest differences were seen in parietal and temporal regions. ¹¹C-PBR28 binding correlated with clinical severity, brain atrophy, and earlier age of symptom onset. ¹¹C-PBR28 binding did not conclusively correlate with amyloid burden as measured with ¹¹C-Pittsburgh Compound B. This study used arterial blood sampling to calculate total distribution volume using the two-tissue compartment model, with correction for free fraction of radioligand. Even after TSPO genotype correction, variance of the PET data was relatively large (coefficient of variance = 34 - 73%).

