3.1 General Design

Subject selection. Patients and controls will be recruited from the ADRC, CUMC clinics, and direct referrals. Target accrual is $n = 4$ completers in each group (DLBD and controls). ADRC subjects who have already undergone GBA and ApoE genotyping through ADRC participation will be preferentially enrolled. If possible, only previously-determined GBA mutation carriers will be included. However, if not enough GBA mutation carriers are recruited to meet target enrollment we will also enroll GBA non-carriers who are also known ApoE4 noncarriers. This strategy is designed to reduce the inclusion of patients with co-existent AD-related tangle pathology, as GBA mutation and ApoE4 non-carrier status are both associated with pure DLBD pathology[14-16]. If we are still unable to meet target enrollment then we will include patients of unknown GBA and ApoE genotype. However, these patients will have ApoE genotyping performed in this study, and we will perform post-hoc analysis to see if ApoE4 status affects ^{11}C -PBR28 binding. ApoE testing will be done for research purposes only and results will not be disclosed to subjects. Subjects must have capacity to provide informed consent and consent will be obtained prior to study procedures.

CONFIDENTIAL

This material is the property of Columbia University Medical Center. Do not disclose or use except as authorized in writing by the study sponsor

Screening procedures. Subjects will undergo screening including history, physical examination, routine laboratory studies, neurological examination and brain MRI. Patients meeting clinical criteria for either dementia with Lewy bodies or Parkinson's disease dementia (collectively considered as DLBD) will be included. Diagnosis will be made via consensus conference using clinical criteria[42]. Screening will also include genetic analysis to exclude subjects homozygous for the rs6971 (Ala147Thr) SNP on the TSPO gene. Homozygous subjects have negligible binding on ^{11}C -PBR28 PET imaging and must be excluded; however, heterozygotes may be included[27, 41]. Clinical evaluation will include Montreal Cognitive Assessment (MoCA), Clinical Dementia Rating scale – sum of boxes (CDR-SB), and Unified Parkinson's Disease Rating Scale (UPDRS).

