Image analysis. PET images will be analyzed using two methods. First, kinetic analysis will be performed using PMOD software (PMOD Technologies). Subject MR images will be coregistered to native space PET images and then segmented to define gray matter regions of interest (ROIs): prefrontal cortex, combined superior and inferior parietal lobule, occipital cortex, inferior temporal cortex, combined middle and superior temporal cortex, hippocampus, parahippocampal gyrus, anterior cingulate, amygdala, insula, and cerebellum. These regions have been selected based on where the largest number of Lewy bodies have been previously reported[45]. The two-tissue kinetic model using time-activity curves from each ROI and the metabolite-corrected arterial input function will be used to calculate total distribution volume, corrected for free fraction of radioligand in plasma (V_T/f_p). Second, the cerebellum will be used as a pseudo-reference region to calculate standardized uptake value ratios (SUVR) for each target ROI. To determine the best time interval for non-invasive measurement of TSPO binding in DLBD, we will calculate SUVR using different time intervals and compute correlation coefficients with the gold-standard measurement V_T/f_p . The time intervals that correspond to SUVR values that have strongest correlation with V_T/f_p will be used to calculate SUVR for the group comparisons between patients with DLBD and controls.

Statistical analysis.

Primary outcome

PET images will be analyzed using 1) the two-tissue kinetic model to calculate total distribution volume, corrected for free fraction of radioligand in plasma (V_T/f_p), and 2) the cerebellum as a pseudo-reference region to calculate standardized uptake value ratios (SUVR). Effect size will be

calculated for different regions as the difference in means (DLBD vs. controls) divided by the standard deviation.

Secondary outcomes

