4.3 Subject Recruitment and Screening

Patients and controls will be recruited from the ADRC, CUMC clinics, and direct referrals. Approximately 50% of enrolled subjects are expected to fail screening procedures or withdraw from the study. We therefore plan to screen 8 subjects in each group to ensure at least 4 in each group complete study procedures. Screening will also include genetic analysis to exclude subjects homozygous for the rs6971 (Ala147Thr) single nucleotide polymorphism on the TSPO gene.

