7.2 Statistical Methods

Primary outcome

PET images will be analyzed using 1) the two-tissue kinetic model to calculate total distribution volume, corrected for free fraction of radioligand in plasma (V_T/f_p), and 2) the cerebellum as a pseudo-reference region to calculate standardized uptake value ratios (SUVR). Effect size will be calculated for different regions as the difference in means (DLBD vs. controls) divided by the standard deviation.

Secondary outcomes

Coefficient of variation (%COV = standard deviation / mean) will be calculated for controls and patients with DLBD for both V_T/f_p and SUVR data. SUVR values will be calculated using cerebellum as reference regions. Additional reference regions will be explored. Correlation coefficients will be computed to look for correlation between ^{11}C -PBR28 binding (V_T/f_p and SUVR) and clinical severity. Severity will be measured using CDR-sum of boxes, MoCA score, and UPDRS. We will also look for correlations between ^{11}C -PBR28 binding and atrophy, as determined using ROI volumes derived from MRI data.

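### The primary effect size is defined with an unnamed standard deviation and no interval; at 4 completers per group, Hedges' g with a 95% confidence interval would tell the R01 designers more from the same data

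*Combined protocol and SAP*

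**What the plan says.** Estimating the DLBD-versus-control effect size is the second primary objective (section 2). Section 1.1 gives its purpose: the pilot data are wanted "to more effectively design an R01 application".

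The estimator is defined once and repeated. Section 7.2 reads "Effect size will be calculated for different regions as the difference in means (DLBD vs. controls) divided by the standard deviation". Section 3.1 and the Study Summary use the same words. None of the three says which standard deviation is meant, and none adds a small-sample correction or a measure of precision. The rule covers both V_T/f_P and SUVR. Section 3.1 lists 11 regions of interest; cerebellum is the SUVR denominator, so 10 remain for that measure.

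On size, section 3.1 sets a target of 4 "completers in each group (DLBD and controls"), and section 4.3 plans to screen 8 per group "to ensure at least 4 in each group complete study procedures". The Study Summary states that the sample is "not expected to provide enough statistical power to see significant group differences".

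On genotype, section 1.1 says "Statistical correction for TSPO genotype allows inclusion of individual heterozygous for the polymorphism", and section 1.4.1.3 describes that correction as the practice in clinical studies. Section 7.2 does not say whether the effect size is calculated before or after it.

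**The concern.** The effect size is one of the pilot's two primary products, and its intended use is to help design a larger study. With 8 completers in all, three things that hardly matter in a large trial start to matter: which SD is the divisor, whether the ratio is corrected for small samples, and whether its uncertainty is shown. A single number per region, without these, could be read as much firmer than it is. The disclosure in the Study Summary concerns the power of a test. It does not tell the reader how imprecise the estimate is.

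**Working it through.** **Inputs.** n = 4 per group (sections 3.1 and 4.3). Effect size 1.5, which section 7.1 quotes from the earlier Alzheimer's study and which serves here only as an example of an observed value. Allele frequency 30% (section 1.4.1.3). Assumed, because the documents do not give them: normal data, equal variances, two-sided 0.05, and a true effect of 0.8 where a true value is needed.

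**The plan's own figure.** Section 7.1 expects significance at an effect size of 1.5 with n = 8. Read as 8 per group, exact t power at two-sided 0.05 is 79.7%, so the figure is reasonable on that reading. At the planned 4 completers per group it is 43.0%.

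**Average bias, pooled SD.** The correction factor is J(v) = Γ(v/2) / [√(v/2) Γ((v-1)/2)]. With v = 4 + 4 - 2 = 6, J = 2 / (1.732 × 1.3293) = 0.869. The expected raw d is the true value divided by J, and 1/0.869 = 1.15, so raw d is about 15% high on average. At a true 0.8:

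| | Mean | Median | RMSE | Median absolute error |
|---|---|---|---|---|
| Raw d | 0.92 | 0.835 (+4%) | 0.94 | 0.53 |
| Hedges' g = J × d | 0.80 | 0.73 (-9%) | 0.81 | 0.47 |

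(Means and medians agree with exact results; the two error columns are from simulation.) The bias is small beside the sampling spread.

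**Imprecision.** With t = d√(n/2), find the noncentralities that place the observed t at the 97.5th and 2.5th percentiles of a noncentral t on 6 df, then divide by √(n/2).
- Observed d = 1.5: t = 1.5 × 1.414 = 2.12; g = 0.869 × 1.5 = 1.30; 95% CI -0.16 to 3.07.
- Observed d = 0.8: g = 0.69; 95% CI -0.68 to 2.23.

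**Why the SD should be named (illustration only).** Take data that give 1.50 with the pooled SD.
- All-subject SD: d/√[(6 + 2d²)/7] = 1.5/√(10.5/7) = 1.22. This version cannot exceed √(7/2) = 1.87, whatever the truth.
- Control-group SD: the ratio to the pooled version is 1/√(2B), with B ~ Beta(1.5, 1.5). Its 10th and 90th percentiles are 0.770 and 1.788, which give 1.15 to 2.68.

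**Genotype.** Under Hardy-Weinberg proportions, with homozygotes excluded, the heterozygous share is 2(0.3)(0.7)/(1 - 0.09) = 0.42/0.91 = 46%. If that share is the same in both groups, the heterozygote counts in two groups of 4 differ in 73% of pilots, and by 2 or more in 29%. With genotype as a covariate, residual df = 5 and J(5) = 0.841, so d = 1.5 becomes g = 1.26. The variance factor of the group contrast is 0.5 + (difference in heterozygote proportions)² / (within-group sum of squares of genotype).
- Counts match: factor 0.50, CI -0.20 to 3.11.
- Counts 1 versus 3: 0.5 + 0.25/1.5 = 0.667, CI -0.39 to 3.28. This split arises in about 12% of pilots.

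The factor must therefore come from the fitted model. Residual SD and df alone would give too narrow an interval when the counts differ.

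**The case against.** The strongest reply is that this is a wording gap in a pilot that is open about its limits. For a two-group mean difference, most readers would take the SD to be the pooled within-group one, and no section suggests otherwise. That stands. The control-SD and all-subject figures show only why one word is worth adding; they do not predict what the sponsor will do.

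Second, much can be rebuilt. Section 7.2 plans the coefficient of variation in each group, so if group means are also reported, each SD is the coefficient times the mean, and an unadjusted effect size with its interval follows. That largely stands. It depends on the means being reported, and it does not recover a genotype-adjusted result.

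Third, the small-sample correction may look like taste, since by median bias g does slightly worse (0.73 against 0.835 for a true 0.8). But g is better on mean bias, on root mean squared error and on median absolute error, so it is more than a preference.

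Fourth, the noncentral-t interval assumes normality, while section 1.4.1.4 reports coefficients of variation of 34 to 73% after genotype correction. At 73% a normal model puts about 8.5% of values below zero (1/0.73 = 1.37 SDs). The interval is thus approximate. It is still more informative than none.

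A reader might infer that the reported effect size is bound to misstate the pilot's result, or that the R01 will be sized from the largest regional value. The documents support neither. The first leans on an SD reading that no section suggests, and no section says how the R01 sample size will be derived.

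**Conclusion.** The point holds as a cheap improvement to a primary output, and not as an error that makes the planned analysis wrong. The SD is unnamed in all three places, and no correction or interval is planned at 4 per group. With the pooled SD the average overstatement is about 15%. Of more consequence is the hidden imprecision: even an observed 1.5 is compatible with true values from slightly below zero to about 3. At an assumed true 0.8, Hedges' g lowers root mean squared error from 0.94 to 0.81, about 14%, with no new data.

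These sizes rest on normality, equal variances and exactly 4 completers per group. The genotype figures also assume Hardy-Weinberg proportions and equal allele frequency in patients and controls.

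**What to change.** In section 7.2, and in the matching text of section 3.1 and the Study Summary:

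- Define the effect size as Hedges' g (pooled within-group SD, small-sample correction) with a 95% noncentral-t confidence interval.
- Report g and its interval for every region on V_T/f_P and, except cerebellum, on SUVR.
- Where the TSPO-genotype correction of sections 1.1 and 1.4.1.3 is applied, take the group contrast, residual SD, degrees of freedom and contrast variance from that one model, and label the result as genotype-adjusted.
- Note that the SUVR intervals do not reflect the choice of time window, which section 3.1 makes from the same data.

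The cost is a few sentences; subjects, scans and measurements do not change. The downside is a smaller, visibly imprecise headline figure, and an estimator whose median lies slightly below the truth.

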7.3 Subject Population(s) for Analysis

Subjects will be age 60 or older. Healthy controls and subjects who meet clinical criteria for DLB or PDD will be included.

8 Safety and Adverse Events

8.1 Definitions

Adverse Event

An *adverse event* (AE) is any symptom, sign, illness or experience that develops or worsens in severity during the course of the study. Intercurrent illnesses or injuries should be regarded as adverse events. Abnormal results of diagnostic procedures are considered to be adverse events if the abnormality:

- results in study withdrawal

CONFIDENTIAL

This material is the property of Columbia University Medical Center. Do not disclose or use except as authorized in writing by the study sponsor

- is associated with a serious adverse event
- is associated with clinical signs or symptoms
- leads to additional treatment or to further diagnostic tests
- is considered by the investigator to be of clinical significance

Event

Adverse events are classified as serious or non-serious. A ***serious adverse event*** is any AE that is:

- fatal
- life-threatening
- requires or prolongs hospital stay
- results in persistent or significant disability or incapacity
- an important medical event

Important medical events are those that may not be immediately life threatening, but are clearly of major clinical significance. They may jeopardize the subject, and may require intervention to prevent one of the other serious outcomes noted above. For example, drug overdose or abuse, a seizure that did not result in in-patient hospitalization, or intensive treatment of bronchospasm in an emergency department would typically be considered serious.

All adverse events that do not meet any of the criteria for serious should be regarded as ***non-serious adverse events***.

Adverse Event Reporting Period

The study period during which adverse events must be reported is normally defined as the period from the initiation of any study procedures to the end of the study treatment followup. For this study, the study drug follow-up is defined as 24 hours following the last administration of study drug.

Preexisting Condition

A preexisting condition is one that is present at the start of the study. A preexisting condition should be recorded as an adverse event if the frequency, intensity, or the character of the condition worsens during the study period.

General Physical Examination Findings

At screening, any clinically significant abnormality should be recorded as a preexisting condition. At the end of the study, any new clinically significant findings/abnormalities that meet the definition of an adverse event must also be recorded and documented as an adverse event.

Post-study Adverse Event

All unresolved adverse events should be followed by the investigator until the events are resolved, the subject is lost to follow-up, or the adverse event is otherwise explained. At the last scheduled visit, the investigator should instruct each subject to report any subsequent event(s) that the subject, or the subject's personal physician, believes might reasonably be related to participation in this study. The investigator should notify the study sponsor of any death or adverse event occurring at any time after a subject has discontinued

or terminated study participation that may reasonably be related to this study. The sponsor should also be notified if the investigator should become aware of the development of cancer or of a congenital anomaly in a subsequently conceived offspring of a subject that has participated in this study.

Abnormal Laboratory Values

A clinical laboratory abnormality should be documented as an adverse event if any one of the following conditions is met:

- The laboratory abnormality is not otherwise refuted by a repeat test to confirm the abnormality
- The abnormality suggests a disease and/or organ toxicity
- The abnormality is of a degree that requires active management; e.g. change of dose, discontinuation of the drug, more frequent follow-up assessments, further diagnostic investigation, etc.

Hospitalization, Prolonged Hospitalization or Surgery

Any adverse event that results in hospitalization or prolonged hospitalization should be documented and reported as a serious adverse event unless specifically instructed otherwise in this protocol. Any condition responsible for surgery should be documented as an adverse event if the condition meets the criteria for an adverse event.

Neither the condition, hospitalization, prolonged hospitalization, nor surgery are reported as an adverse event in the following circumstances:

- Hospitalization or prolonged hospitalization for diagnostic or elective surgical procedures for a preexisting condition. Surgery should **not** be reported as an outcome of an adverse event if the purpose of the surgery was elective or diagnostic and the outcome was uneventful.
- Hospitalization or prolonged hospitalization required to allow efficacy measurement for the study.
- Hospitalization or prolonged hospitalization for therapy of the target disease of the study, unless it is a worsening or increase in frequency of hospital admissions as judged by the clinical investigator.

